Eye exams: All infants will get eye exams according to standard NICU protocols. Serial eye exams will be performed according to the usual intervals, which is until retinal vascularization has matured or active ROP has stabilized, usually at 1-2 months post-term. The area of vascularized retina, clock hours of neovascularization, and amount of retinal vascular dilation and tortuosity will be measured by indirect ophthalmoscopy in all infants at each clinical exam by an ophthalmologist masked to the treatment group. Stage of retinopathy of prematurity and need for ROP treatments will be measured at 40 weeks gestation plus or minus three weeks and followed over time. Infants with ROP will be monitored over time for longer term visual and anatomic outcomes. For both groups, infants will have SOC eye examinations prior to discharge around 40 weeks GA (≥ 38 wks GA). For both groups, if infant is discharged prior to 38 weeks GA, we will collect follow-up data from their outpatient follow-up eye exam from UCSD or other provider

Nutrition: Omegaven has been approved by the FDA for use in children and infants with parenteral nutrition associated liver disease (PNALD). In this study we intend to use Omegaven under an IND exemption to study the use of the drug in reducing the incidence and severity of retinopathy of prematurity (ROP). Our aim is to differentiate the phospholipid profiles and gene expression pathways of at-risk very low birth weight infants with and without treatment with Omegaven® (high n-3 fish oil supplement) and to establish whether omega-3 fatty acid supplementation in extremely low birth weight infants will reduce the incidence and severity of retinopathy of prematurity (ROP). The study intervention “drug product” has been used in the neonatal population via the same route of administration safely for other disease indications internationally and nationally including here at University of California San Diego. This investigation does not significantly increase the risk or decrease the acceptability of risk of our study population.

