The investigational drug pharmacy (IDS) will obtain the Omegaven and dispense it to the nurse for administration in a separate line than the rest of the nutrition (amino acids, sugars, etc). The NICU nutritionist will optimize the total nutritional calories to the infant per NICU protocols. The IDS pharmacist, nutritionist, and NICU team will not be blinded to ensure that the infant in the Omegaven group meets all the nutritional requirements as determined by the NICU neonatology attendings and fellows involved in the study. The ophthalmology team will be blinded to the treatment group to prevent any potential for bias during the eye exam.

Outcome Measures:

Outcome 1: Change in concentrations of basic fatty acids (EPA, DHA, and AA) and their bioactive metabolites will be assessed at multiple time points.

Outcome 2: Change in mRNA expression of TNF- α , PPAR- γ , and VEGF at multiple time points.

Outcome 3: Severity stage of ROP in Group 1 compared to Group 2. This will be assessed at the time of ROP screening (approximately 31 weeks), and the outcome will be measured at approximately 40 weeks adjusted age. The stage of ROP at 40 weeks adjusted will be used for statistical analyses.

Safety:

A data safety monitoring board (DSMB) will be established to monitor the safety of enrolled infants in the study as well as identifying the efficacy of the treatment at ongoing intervals. The DSMB will meet after the first 5 infants are enrolled and then regularly at multiple intervals during the study. Clinical safety assessments will occur during the hospital admission including vital signs, weight, physical exam and laboratory assessments of triglycerides. The neonatologist will review the assessments and determine if the subject should remain in the study or be removed.

Statistical Analysis

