Our primary analytic approach will use generalized linear mixed models (GLMM). These methods will address problems of missing data, variable timing of the subject visits, and other possible unintended violations of design. Although our retention and follow-up plan is designed to minimize missing data, an advantage of the GLM models is that they allow us to maximize statistical power by not excluding subjects with some missing data. More specifically, GLM assumes that the data can be missing at random (MAR) or missing completely at random (MCAR). The benefit of this assumption is with a repeated measure problem (e.g., longitudinal data) you can still analyze data from all subjects, even if some have missing data (assumed MAR or MCAR). Mixed regressions will also allow us to estimate an intercept and slope for each patient based on all available data for that individual augmented by the data from the entire sample, with two random effects being used to model time trends (i.e., a random intercept and a linear trend). Further details of selected analyses related to each outcome are provided next.

For Outcome (a-b), the primary outcome is DHA at a specified period of time (i.e. 40 weeks) to assess the basic fatty acids. Outcome (a) posits that patients in Group 1 will differ from those in Group 2 with respect to i) DHA

ii) EPA iii) AA iv) bioactive metabolites. To assess Outcome (a) (i.e. to evaluate the effects of group, time, and their interaction on the change from baseline DHA measurements), a mixed effects model with group (IV Omegaven then PO baby fish oil or Intralipid), time, and group by time interaction as fixed effects, and random intercept and slope to account for within subject correlation. We expect that the interaction in question will be significant.

For Outcome (c), we hypothesize that Group 1 and Group 2 will have a different severity stage of ROP. To assess Outcome (c), we will use a *Mixed-effects ordinal logistic regression model* with severity stage of ROP after 40 weeks (Stage I, II, III, IV, V) as the outcome variable. The same fixed and random effects mentioned above will be used in evaluating Outcome(c).

All statistical analyses will be performed using SAS software version 9.3 (SAS Institute, Cary, North Carolina, USA).

[figure not shown]
Power Calculations

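### The planned ROP model covers Stages I to V with no level for infants without ROP, so the incidence aim has no analysis; it also puts repeated-measures terms on a stage taken at one time point

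*Combined protocol and SAP*

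**What the plan says.** All references are to the combined protocol and SAP.

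- **Section 6, Specific Aims:** the second aim covers both incidence and severity of ROP. Section 9 (Nutrition) repeats it.
- **Section 9, Outcome Measures:** Outcome 3 is severity stage only. It says "the outcome will be measured at approximately 40 weeks adjusted age" and "The stage of ROP at 40 weeks adjusted will be used for statistical analyses".
- **Section 9, Statistical Analysis, Outcome (c):** a mixed-effects ordinal logistic model takes "severity stage of ROP after 40 weeks (Stage I, II, III, IV, V) as the outcome variable". On model terms it says "The same fixed and random effects mentioned above will be used in evaluating Outcome(c"). Those terms, set out for Outcome (a), are group, time and "group by time interaction as fixed effects, and random intercept and slope to account for within subject correlation".
- **Section 9, Eye exams:** infants are examined serially "until retinal vascularization has matured or active ROP has stabilized", and "Stage of retinopathy of prematurity and need for ROP treatments will be measured at 40 weeks gestation plus or minus three weeks".
- **Section 10, inclusion criteria:** entry is by gestational age or birth weight. ROP is not an entry criterion.
- **Section 5, lay summary:** the blood studies will compare infants who have ROP with infants who do not.

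**The concern.** Some infants will have no ROP stage to enter, and the listed levels give them nowhere to go. An analyst who follows the text drops them, which has two consequences. The incidence half of the aim is never tested. The severity comparison also loses the protection of randomisation, because membership of the staged subgroup depends on an outcome that treatment may alter.

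The model terms raise a second problem. Time, group-by-time, random intercept and random slope suit DHA, which is measured repeatedly. Outcome Measures restricts the ROP analysis to the stage at 40 weeks. The two statements do not fit together, so the ROP model is not determined by the plan. The trial's title is about preventing ROP, so this analysis will be read closely even though DHA is the primary outcome.

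**Working it through.** **1. The plan's own figure.** The only power figure is for DHA: difference 42 − 27 = 15, SD 15, 20 per arm, two-sided 0.05. The noncentrality is 15 / (15 × √(2/20)) = 3.16 on 38 degrees of freedom, which gives power 0.87. This agrees with the stated figure of over 80%. It says nothing about ROP, for which no power is given.

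**2. Levels against aim.** The aim needs incidence and severity. The model has Stages I to V. No section gives a no-ROP level, a binary ROP endpoint, or an analysis of need for treatment. The incidence aim therefore has no stated analysis.

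**3. Model terms against data.** Take one record per infant.
- If every exam falls at exactly 40 weeks, the fixed columns (intercept, group, time, group × time) have rank 2 of 4.
- If exam dates vary over 37 to 43 weeks, the rank is 4 of 4. Group-by-time then describes how the group difference varies with exam date between infants, which is not the treatment effect.
- In both cases there are no repeated values within an infant from which to estimate a slope.

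**4. Size of the effect on power.** The documents give no stage distribution, so these are assumptions: 20 per arm; 40-80% of controls with a stage; a Stage I/II/III mix of 40/35/25 or 60/30/10, or Stage III set to 31.4% of controls; no Stage IV or V. The only ROP rates in the documents are the cited laser rates in section 7: 9/60 = 15.0% and 22/70 = 31.4%. They give an odds ratio of (9/51)/(22/48) = 0.385. Applying it to stage is also an assumption. The test is a tie-corrected rank test (the proportional-odds score test), not the planned mixed model, with 20,000 runs per cell.

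| Scenario | Staged infants of 40 | Power, I-V only | Power, with no-ROP level | Binary any-ROP (chi-square) |
|---|---|---|---|---|
| A. Common odds ratio 0.385 | 12-28 | 4-16% | 27-37% | 28-30% |
| B. Every stage halved (incidence only) | 12-24 | 3-5% | 27-66% | 29-75% |
| C. Lower stage among affected only | 16-32 | 11-29% | 5-17% | 4-5% (no incidence difference) |

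**5. Why the subgroup distorts.** In A, with p the share of controls who are staged, the odds ratio among staged infants is 1 − p(1 − 0.385). This is 1 − 0.4 × 0.615 = 0.754 at p = 0.4 and 1 − 0.8 × 0.615 = 0.508 at p = 0.8, both weaker than the true 0.385. In B it is exactly 1, so the Stage I-V model has nothing to detect. In C it stays at 0.385.

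**6. At the enrolment target.** Section 9 (Power Calculations) takes 40 as completers and enrols 60. At 30 per arm, scenario B with 80% control incidence gives about 90% for the binary test and 82-84% for the ordinal test with the no-ROP level. Scenarios A and C stay below 80%.

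**The case against.** **A level zero is obviously meant, and only selected analyses are detailed.** Both may be true. But the five levels are listed explicitly, and no incidence analysis is written elsewhere. A reader might infer that the sponsor means to exclude unaffected infants; the documents do not show that intent. The gap is in what is written, and it leaves the coding to be chosen after data are seen.

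**The mixed model handles missing data.** The plan says "GLM assumes that the data can be missing at random (MAR) or missing completely at random (MCAR"). It does not apply this to unstaged infants, and it would not help them: their stage is absent because of the outcome itself.

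**Serial exams exist, so a longitudinal model is possible.** It is, but Outcome Measures restricts the analysis to the 40-week stage. One of the two statements must change.

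**The model is not wholly inestimable.** This stands. A reader might infer that nothing in it can be fitted. With varying exam dates the fixed terms can be estimated. If each eye were a record, a random intercept could be too; the plan does not say whether the unit is the eye or the infant. What fails is the within-infant slope and the interpretation of group-by-time.

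**The power figures are mostly assumed.** This also stands. They illustrate the consequence, while the textual gap needs no simulation.

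**Conclusion.** The point holds as written in the plan: half of the second aim has no analysis, and the ROP model does not match the single time point allowed for it. It should be fixed before analysis. The primary DHA outcome is not affected.

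The size depends on how treatment works. Under the assumptions above and at 20 per arm, the Stage I-V model misses a pure incidence effect and weakens a common odds ratio. It is not always the weaker choice: if treatment changes severity only, it has more power.

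Three stronger readings are not supported.
- A reader might infer that no ROP analysis could reach 80% power. That is true of these scenarios only at 20 per arm; at 30 per arm, halving an 80% incidence passes 80%.
- A reader might take any ROP at the 40-week exam as incidence. It is prevalence at one exam. Screening starts at about 31 weeks, and ROP may have regressed or been treated by then.
- The mismatch between a stage after 40 weeks (Statistical Analysis) and one at about 40 weeks or within three weeks of it (Outcome Measures, Eye exams) is a matter of wording. The latter two agree.

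**What to change.** 1. **Levels.** In Statistical Analysis, Outcome (c), add no ROP as the lowest level (0, I to V), so that every randomised infant with the eye exam is analysed.
2. **Incidence.** Add a between-arm comparison of any ROP recorded at any of the serial exams already planned. State in advance how infants whose ROP regressed or was treated before the 40-week exam are classified, so that they are not counted as never having had ROP. Report need for ROP treatment, already collected, by arm.
3. **Model.** With the 40-week stage as endpoint, fit a proportional-odds model with group and the gestational-age randomisation factor, without time, group-by-time or random slope. Allow for twins randomised together (for example, cluster-robust standard errors by family). State whether the unit is the infant (for example, worse eye) or the eye. If repeated exams are meant, correct Outcome Measures instead; the no-ROP level is still needed.
4. **Wording.** Use one time window in Eye exams, Outcome Measures and Statistical Analysis, and label the ROP results exploratory.

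**Cost.** Rewording in three places, one more level, one 2×2 comparison and one classification rule, all on data already collected. The trade-off is the lower power in the severity-only case (scenario C). Stage among affected infants should therefore also be tabulated by arm, labelled as a comparison not protected by randomisation.

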10. HUMAN SUBJECTS

The University of California, San Diego (UCSD) is the only site participating in this study.

We anticipate enrolling 60 infants and up to 60 mothers at UCSD. We will consider patients for enrollment into this study for 5 years.

INFANT:

Inclusion Criteria:

- Infants born \geq 23 weeks gestation and \leq 30 weeks gestation or less than 1500 g at birth.
- Infant whose parent or guardian signed the written consent and HIPAA form.

Exclusion Criteria:

- Patients with liver disease attributable to known causes (i.e. genetic disease, hepatitis) and/or bleeding or clotting abnormalities will be excluded as shown by LFTs.
- Infants $<$ 23 weeks gestation

MOTHER:

- Any mother 18 years of age or older that allows their infant to be enrolled.
- Proficiently English speaking/reading and can complete questionnaire

Infants may still be enrolled in this study if the mother declines to be also participate in the study.

Participation in research is entirely voluntary. Parents of subject may refuse to participate or withdraw at any time without penalty or loss of benefits to which they are entitled. If the parent of subject decides that he/she no longer wishes to continue in this study, the subject's parents will be required to notify the study doctors, [name] or her research staff by calling her at [contact].

The study doctor may decide to take the subject off of the study without the parent's consent if:

- Subject is unable to meet the requirements of the study;
- Subject's medical condition changes;
- New information becomes available that indicates that participation in this study is not in the subject's best interest;
- If the study is stopped,
- The sponsor of the study or the competent authority has the right to withdraw the subject from the study without the parent's permission,
- The study physician can withdraw the subject from the study without the parent's consent if he/she comes to the conclusion that further participation is not in subject's best interest. This can be due to disease or side effects or because subject does not comply with study procedures

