7. BACKGROUND AND SIGNIFICANCE

Clinical:

Approximately 517,000 infants are born prematurely every year¹, and as low birth weight and premature infants are surviving longer, they are at high risk of developing severe ROP. In the United States, 2,000 infants per year are diagnosed with severe ROP, which is the leading cause of irreversible childhood blindness in the United States. In our NICU, we care for between 60 and 80 infants each year that are born with low birth weight.

Usual parenteral nutrition protocols do not meet the infants' fetal accretion rates. Despite receiving 14-28 mg DHA/kg/day,² preterm infants have lower serum DHA and EPA levels than they would have had *in utero*, and

their tissues have lower n-3 and n-6 fatty acid than full term infants, indicating that their dietary needs are often not met.³ Preterm and small for gestational age infants have altered serum phospholipid fatty acid profiles with lower DHA and polyunsaturated omega-3 fatty acids than appropriate for gestational age infants.⁴ Low birth weight infants often have severe lung disease and are exposed to exogenous oxygen, which causes retinal blood vessel attenuation, retinal hypoxia, up regulation of pro-angiogenic factors, and neovascularization, which can lead to irreversible vision loss.

In a recent Polish prospective interventional study, Pawlik et al. showed that in preterm infants (average 28 week gestation, 935 gram birth weight), continuous intravenous n-3 fatty acids with Omegaven® from day one to day 28 of life, followed by enteral omega-3 fatty acids is safe and resulted in a significantly decreased need for ROP laser treatment. In the treatment group, 9 of 60 infants needed laser compared with 22 of 70 infants in the control group.^{7,12} On treatment, infants had higher plasma and red blood cell DHA levels at 7 and 14 days and a lower risk for cholestasis. This study showed that treatment was well tolerated in preterm infants and that Omegaven® has a positive effect on ROP pathogenesis, but no investigations were done into the mechanisms by which ROP was suppressed in the experimental group compared with the control arm. There is also no clinical data that currently differentiates the differences in the blood biology (fatty acids, gene expression, and proteins) in infants with and without severe ROP.

Translational:

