9. RESEARCH DESIGN AND METHODS

The treatment duration for the study will begin 0-7 days of life and continue until 40 weeks adjusted age (full-term). Intravenous treatment will start in the first few days of life and will continue until the infant can tolerate enteral nutrition. Once enteral feeds can be started, supplementation by mouth will begin until 40 weeks adjusted age.

Laboratory blood draws:

Prior to enrollment: In addition to routine tests, blood will be tested for AST and ALT. If these tests are interpreted as abnormal, the infant will not be considered for enrollment in the study as it will be deemed a contraindication to supplemental Omegaven.

While the infant is growing in the hospital, the doctors will need to check the infant's blood to make sure the infant is developing as expected.

If the infant is enrolled in the study, the infant will be randomized in blocks of 4 by gestational age to one of two groups. The control group will get standard of care nutrition, and the experimental group will get standard of care nutrition with supplemental omega-3 fatty acids. Soon after birth, most premature infants need additional nutrition through the vein (intravenous). For the control group, there will be no changes to the standard of care parenteral nutrition. For the experimental group, the infant will receive Omegaven, an intravenous lipid preparation prepared from highly refined fish oil, in addition to the standard of care parenteral nutrition. In the instance that twins are enrolled in the study, the siblings will be randomized as one to receive the same treatment per request and approval from [name].

Transition – For the second/interventional group, Omegaven will be stopped once enteral feeds are at 120 ml/kg and enteral Oil will be started. There will be no overlap of parenteral and enteral n-3 supplementation.

If the infant can start using his/her own stomach for digestion, he/she will get fatty acid supplementation. In the control group, the infant will receive standard of care feeding. If the infant is in the experimental group, the infant will get one fourth (1/4) teaspoon per kilogram per day ($1.25\text{mL/kg/day} = 400\text{ mg omega3 per kg of fish oil per day}$) of Carlson's fish oil oral solution. Dose will be divided to at least twice a day dosing for better tolerance.

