11. RECRUITMENT

Waiver of Consent for Aiding in Research Recruitment:

I am asking for a waiver of consent while recruiting subjects because:

It would be minimal risk to the potential subjects while reviewing their private information. For this study, the subjects will already be hospitalized. The PI or sub PI will need to review the subjects' medical records for their routine care and to determine treatment for the subjects. While reviewing the medical records for their standard of care (SOC) treatment, the PI or sub PI may determine that the subject may qualify for the study and then proceed to ask the subject if they would be interested. The PI or sub PI will not review a patient's medical record solely to determine if they qualify for this study.

Reviewing patients' medical records would not adversely affect the rights and welfare of the potential subjects because the patients have already signed a HIPPA form when they were admitted to the hospital. Because the patient signed the form, we are allowed to review their medical records.

We would not be able to determine if the patient qualifies for this study without reviewing their medical records.

We will provide any new pertinent information to the subjects by providing the subject an addendum consent form with the information about this study. The patient will have time review and ask questions before signing the addendum and will be able to withdraw their consent if they desire.

I am asking for a waiver of HIPAA Authorization while recruiting subjects because:

The research staff will only print out medical records from patients when they have signed the consent form and the HIPAA consent form. If we do print out medical records, we will immediately black out any PHI on the documents, then copy the documents, and then again black out any PHI. The charts will be kept in a locked office in a locked cabinet and only the research staff assigned to the study will have access to the charts.

We would not be able to determine if the patient qualifies for this study without reviewing their medical records including their PHI (for example we will need contact information and mailing information).

The benefit of allowing access to the patient's PHI, will allow us to determine if they qualify for this study (for example their birth weight or gestational age).

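### Neither the DHA model nor the ROP model adjusts for gestational age or birth weight, so the plan has no pre-specified answer to a chance imbalance in size for gestation; this matters mainly for ROP

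*Combined protocol and SAP*

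**What the plan says.** - **Entry (section 10, infant inclusion criteria).** An infant qualifies from 23 weeks up to "30 weeks gestation or less than 1500 g at birth". Read as written, the weight route has no upper gestational limit.
- **Randomisation (section 9).** "the infant will be randomized in blocks of 4 by gestational age to one of two groups". Birth weight is not named as a factor.
- **DHA model (section 9, Statistical Analysis, Outcome (a)).** The terms are group, "time, and group by time interaction as fixed effects, and random intercept and slope to account for within subject correlation". The plan expects the group-by-time interaction to be significant, so that is the term it tests.
- **ROP model (Outcome (c)).** "The same fixed and random effects mentioned above will be used in evaluating Outcome(c". Section 9, Outcome Measures, takes stage at 40 weeks adjusted age as the value analysed.
- **Background (section 7).** "Preterm and small for gestational age infants have altered serum phospholipid fatty acid profiles with lower DHA". The same section ties low birth weight, together with prematurity, to a high risk of severe ROP.
- **Availability (section 11).** Records are reviewed for eligibility, "for example their birth weight or gestational age", so both values are known at entry.

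No covariate-adjusted or sensitivity analysis is described.

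**The concern.** With two entry routes joined by an *or*, gestational age alone does not describe the sample. Two infants of the same gestation can differ widely in weight, and an infant born later than 30 weeks enters only if its weight is under 1500 g. The protocol's own background presents size as relevant to both outcomes. Blocking on gestational age cannot balance size for gestation, and the models as written cannot allow for it.

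Two things are at stake. One is precision: any outcome variation that gestational age and size explain stays in the error. The other is credibility: if one arm turns out to hold more small-for-gestation infants, an adjustment chosen after the results are known will persuade nobody. DHA has a baseline value that takes up some of the difference between infants. ROP has none, and it has no power calculation either.

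**Working it through.** **Inputs from section 9, Power Calculations.** Two-sided 0.05; N = 40, equally split, so 20 per arm; mean pre-post DHA differences 42 and 27 µmol/L, so a difference of 15; largest SD considered 15; about 60 enrolled, so 60/2 = 30 per arm.

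**Assumptions (the documents give no figures).** Share of infants small for gestation 15%, 25% or 35%; correlation r of the size measure with DHA change 0.2 to 0.5; correlation ρ of raw birth weight with gestational age 0.5 or 0.7; ROP odds ratio 1.5, 2 or 3 per SD of the size measure.

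**1. The plan's own figures.** Noncentrality = 15 / (15 × √(2/20)) = 3.16 on 38 df, which gives power of 86.9%. This agrees with the stated figure of over 80%. The accrual target follows from 40 / (1 − 1/3) = 60.

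**2. Chance imbalance in small-for-gestation infants.** With X₁ and X₂ independent Binomial(n, p), find P(|X₁ − X₂| ≥ 0.2n). That is 4 or more infants at n = 20 and 6 or more at n = 30.

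| Assumed share | 20 per arm | 30 per arm |
|---|---|---|
| 15% | 11.8% | 4.6% |
| 25% | 19.9% | 10.0% |
| 35% | 24.5% | 13.6% |

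**3. The same for a continuous size measure.** The standardised arm difference has SD √(2/n), which is 0.316 at n = 20. It exceeds 0.3 SD in 34% of trials and 0.5 SD in 11%. At n = 30 these become 25% and 5%.

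**4. How far blocking helps raw birth weight.** If gestational age were fully balanced, the SD in step 3 shrinks by √(1 − ρ²). At 20 per arm the chance of a difference above 0.5 SD falls from 11.4% to 6.8% (ρ = 0.5) or 2.7% (ρ = 0.7). This discount applies to raw weight, not to a weight-for-gestation z-score.

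**5. Size of the effect on DHA.** A 0.5 SD imbalance shifts the unadjusted difference in change by r × 0.5 × 15, which is 1.5, 2.25 or 3.75 µmol/L at r = 0.2, 0.3 or 0.5, against a planned 15. If a single change score were analysed, adjustment would lower the difference detectable with 80% power from 13.64 to 13.01 (r = 0.3) or 11.81 (r = 0.5), ignoring the degree of freedom spent.

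**6. Which term does the work in the DHA model.** The tested quantity is a difference in slopes. A covariate that is constant over time, entered as a main effect, explains differences in level. With complete data on a common visit schedule it leaves the group-by-time estimate unchanged. A simulation of the planned model (20 per arm, four complete visits, size assumed to affect the slope) shows this. The group-by-time estimate moved 1.47 units per SD of imbalance both without and with the main effect, and its standard error was 1.272 both times. Adding the size-by-time term reduced the movement to about −0.09.

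**7. Precision for ROP (illustrative).** Simulated proportional-odds trials with 20 per arm, four ordered levels, an assumed treatment odds ratio of 0.25 and 1,500 trials per setting gave:

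| Covariate odds ratio per SD | Unadjusted power | Adjusted power |
|---|---|---|
| 1.5 | 56.5% | 57.1% |
| 2 | 50.7% | 55.4% |
| 3 | 45.3% | 53.9% |

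The Monte Carlo standard error of each figure is about √(0.5 × 0.5 / 1500) = 1.3 points. The plan lists five stages, and the simulation has no gestational-age blocks. The gap between the columns is therefore informative about direction and rough size, and the power levels themselves are not a forecast for this trial.

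**The case against.** The strongest reply is that randomisation already protects the comparison. That is right. The unadjusted tests are valid, and a reader who infers that the DHA or ROP estimates are biased by design would go further than the documents allow.

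A reader might also infer that birth weight is left wholly to chance among 20 infants per arm. The documents do not support that either. Blocking on gestational age balances raw weight in part (step 4). Twenty is the completer target, about 30 per arm are to be randomised, and the mixed model is chosen so that infants with partial data are kept. What blocking cannot balance is size for gestation.

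The documentary link is also limited. For DHA, section 7 speaks of lower levels, whereas the model analyses change from baseline, although the analysis section also names DHA at 40 weeks as primary. For ROP, section 7 names low weight and prematurity jointly and shows no effect of weight beyond gestation. Every covariate strength used above is assumed, and at the weakest the ROP gain is negligible. DHA power is already 87% at the largest SD considered, so DHA does not need the adjustment to reach its target.

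Finally, it is tempting to suppose that adding birth weight as one main effect would settle the matter. It would not. It leaves the tested DHA interaction as it was (step 6), and raw weight without gestational age mixes maturity with size. These replies reduce the size of the point and change its remedy. They do not supply the missing pre-specification.

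**Conclusion.** The point holds as one of precision and pre-specification, not of validity. Entry is by gestation or weight, allocation is blocked on gestation alone, and neither model contains either variable. A difference between arms of 20 percentage points or more in small-for-gestation infants is a minority event, but not a rare one: 12% to 25% of trials among 20 completers per arm, or 5% to 14% among 30 randomised per arm, for assumed shares of 15% to 35%. The gain from adjustment runs from negligible to modest, depending on covariate strengths that the documents do not give. It matters mainly for ROP, which has no baseline value. For DHA the benefit is smaller and comes only if the covariates are allowed to act on the time trend.

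**What to change.** In section 9, Statistical Analysis, before any outcome is compared by arm:

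- Name two baseline covariates for both models: gestational age (the blocking factor) and birth-weight-for-gestation z-score. State the reference chart, so that no choice between size measures remains open.
- In the ROP ordinal model, enter both as main effects.
- In the DHA mixed model, enter both together with their interactions with time.
- Make the adjusted analysis primary and report the unadjusted result alongside. State that the adjusted and unadjusted ROP odds ratios estimate different quantities, so a difference between them is not in itself evidence of imbalance.

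The cost is one or two sentences. Entered as linear terms, the covariates use two degrees of freedom in the ROP model and four in the DHA model (two main effects and two time interactions, with time linear). No new data, visits or patients are needed.
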